5.3.2. Justification for Use of Placebo Investigational Medicinal Product

A placebo-controlled design is appropriate, given the purpose and objectives of this clinical study. Inclusion of a placebo control group is consistent with guidelines for controlled trials of prophylactic treatment of migraine in adults (Silberstein, 2008) and the Classification Committee of the IHS guidelines for controlled trials of drugs in migraine, 3rd edition (Tfelt-Hansen, 2012).

5.4. Other Medicinal Products/Non-Investigational Medicinal Products

Not applicable.

5.5. Treatment after the End of the Study

At the end of the last study visit, patients will return to the care of their treating physicians.

No treatment is planned by the sponsor after completion of the study. Patients should be treated with standard of care after withdrawal from or termination of the study, as appropriate.

5.6. Restrictions

Patients will be required to comply with the following restrictions.

5.6.1. Activity

Patients must remain at the site, for safety observation, at least 60 minutes after injection or according to medical judgment.

5.6.2. Blood Donation

Patients may not donate blood while taking IMP and for 5 half-lives (6.0 months) after the last IMP administration.

5.6.3. Pregnancy

Restrictions in regard to pregnancy and required laboratory values (ie, serum and urine β -HCG tests) are provided in the inclusion and exclusion criteria (Section 4.1 and Section 4.2, respectively). Restrictions in regard to contraception methods are reviewed in [Appendix E](#).

5.7. Prior and Concomitant Medication or Therapy

Any prior or concomitant medication, treatment, psychotherapy, or procedure a patient has had for migraine and/or depression within the past 10 years or for any indication within the past 5 months before IMP administration and up to the end of study, including follow-up, will be recorded on the eCRF. Trade name and international nonproprietary name (if available), indication, dose, and start and end dates of the administered medication or treatment will be recorded. In addition, migraine and depression preventive medication listed in [Appendix G](#) that a patient took before study drug administration will be recorded on the eCRF. Generic or trade name, indication, and dosage will be recorded. The sponsor will encode all medication according to the World Health Organization drug dictionary (WHO Drug).

For migraine, patients using no more than 1 preventive medication at the time of the screening visit (V1) will be allowed to remain on the medication. The total number of patients receiving concomitant migraine preventive medication during the study will not exceed 30% of the total sample size of the study. For depression, patients using no more than 1 medication for the treatment of depression at the time of the screening visit (V1) will be allowed to remain on the medication. Patients on a concomitant migraine preventive medication and/or an antidepressant must be on a stable dose for at least 8 weeks of consecutive use prior to study entry (ie, before the 28-day baseline period), without anticipated changes during the study. If in the clinical

judgment of the investigator or qualified psychiatrist, the patient's antidepressant medication needs to be changed or dose-adjusted during the 28-day baseline period, the patient will be screen failed. Any changes made during the treatment period will be recorded in the electronic data capture system. The percentage of patients with these changes will be analyzed at the end of the study.

All concomitant medications prescribed or over-the-counter medications, vitamins, or herbal or nutritional supplements, must be recorded with indication, daily dose, and start and stop dates of administration. All patients will be questioned about concomitant medication use at each visit. Complete discontinuation criteria are provided in Section 4.3.

A list of preventive migraine medications that are allowed for up to 30% of the study population and antidepressant medications allowed for the whole study population for the duration of the study are given in [Appendix G](#).

Concomitant medications that are not allowed for the duration of the study include other monoclonal antibodies that target the CGRP pathway (erenumab, eptinezumab, or galcanezumab), as described in Section 4.2.

If clinically indicated, patients' antidepressant medications and psychotherapy may be changed at any time during the treatment period at the discretion of the investigator, and all changes will be recorded in the eCRF. In such case, the patient's continued participation in the study will be reviewed by the medical monitors.

At each visit at the investigational center after the screening visit (V1), the investigator will ask patients whether they have taken any medications (other than IMP), including over-the-counter medications, vitamins, or herbal or nutritional supplements, or received any therapies (eg, ECT) since the previous visit.

Concomitant medication and treatment, including psychotherapy, will be recorded until visit 6, day 169.

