1.2.2.2. Clinical Safety and Efficacy Studies

The safety, tolerability, and efficacy of fremanezumab have been evaluated in 2 completed Phase 2b studies (Studies LBR-101-021 and LBR-101-022) in patients with migraine (Bigal, 2015a; Bigal, 2015b). The results of both studies showed fremanezumab to be superior to placebo for primary and secondary endpoints (benefit at 3 months of therapy).

Fremanezumab was well tolerated with favorable safety profile across the 8 completed Phase 1 studies, 2 completed Phase 2b studies, and 2 completed Phase 3 studies in patients with migraine. The treatment-emergent adverse events reported in the Phase 1, Phase 2b, and Phase 3 studies were predominantly mild to moderate in severity. A specific “pattern of adverse events” that

could be associated with a dose or a dose range of fremanezumab has not been identified, nor has a maximally tolerated dose been identified. Overall, the nature and occurrence of the reported treatment-related adverse events across the clinical program have not raised any specific safety concerns.

Two pivotal Phase 3 studies in CM and EM patients (Studies TV48125-CNS-30049 and TV48125-CNS-30050), confirmed efficacy findings in Phase 2. Study TV48125-CNS-30049 was a 16-week, multicenter, randomized, double-blind, placebo-controlled, parallel-group study to compare the efficacy, safety, and tolerability of 2 dose regimens of sc fremanezumab (fremanezumab 675 mg quarterly [675 mg/placebo/placebo; N=379] and a starting dose of fremanezumab 675 mg followed by fremanezumab 225 mg monthly [675/225/225 mg; N=376]) and placebo (N=375) in adults (18 through 70 years of age) with CM. Patients who were on monotherapy (79%) and patients on stable doses of preventive medications (21%) were included in the study. The study consisted of a screening visit, a baseline period lasting approximately 4 weeks (~28 days), and a treatment period lasting approximately 12 weeks.

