5.9. Randomization and Blinding

After the 28-day baseline period, the first 12 weeks of this study will be double-blind. Patients and investigators will remain blinded to IMP assignment during this part of the study. This will be followed by a 12-week open-label extension phase.

Patients will receive 225 mg sc fremanezumab (visit 2, visit 3, and visit 4) or matching placebo (visit 2) in monthly doses.

For the first phase of this study, the sponsor, investigators, study staff, and patients will be blinded to treatment assignment. A computer-generated master randomization list will be provided to drug packaging facilities. The packaging vendor(s) will package active drug and placebo into single-visit kits according to Good Manufacturing Practice procedures. Kits will be identical in appearance and contain 1 prefilled syringe with either active drug or placebo.

Patients will be stratified based on sex, country, migraine classification (ie, CM or EM), and PHQ-9 score category (10 to 14, 15 to 19, and ≥ 20) to ensure balance for the covariates.

Patients will be randomly assigned to treatment groups by means of a computer-generated randomization list using electronic IRT. This system is used to ensure a balance across treatment groups. The specifications for randomization will be under the responsibility and oversight of Teva Global Statistics.

At randomization visit (day 1), each patient will be randomized in a 1:1 ratio within the stratum to which he or she belongs to receive monthly 225 mg sc fremanezumab or placebo, as assigned by the IRT. In the open-label extension phase starting at week 12, however, all patients will receive active treatment with a quarterly dose of 675 mg sc fremanezumab.

The IRT will manage initial drug supply, maintenance of adequate study drug supplies on site, and study randomization centrally. At each study visit where study drug is administered, the IRT will be queried, the site personnel will retrieve the study drug from refrigerated storage, and the patient will self-administer treatment with the 1 or 3 prefilled syringes, depending on the study visit, contained in the appropriately numbered kit.

The sponsor's clinical personnel (and delegates) involved in the study will be blinded to the identity of the IMPs until the database is locked for analysis and the IMP assignment is known. However, if a prioritized sample analysis is needed, bioanalytical and clinical pharmacology personnel may be unblinded.

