9.1. Sample Size and Power Considerations

A sample size of 288 (144 per treatment group) evaluable patients completing the study will provide 90% power to detect a treatment difference of 2 days with a common standard deviation of 5.2 days in changes from the 28-day baseline period in monthly average migraine days between active and placebo groups at a 2-sided alpha level of 0.05. This sample size will provide approximately 80% power to detect a treatment difference of 2 points with a common standard deviation of 6 points in the change from randomization visit (day 1) in HAM-D 17 total score at a 2-sided alpha level of 0.05. Assuming a 15% drop-out rate, approximately 340 patients (approximately 170 patients per treatment group) will be randomized.

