### 6.2.2. Primary Efficacy Analysis

The hypothesis testing for the primary analysis is:

$$H_o : \delta_1 = \delta_2 \quad vs \quad H_a : \delta_1 \neq \delta_2$$

where  $\delta_1$  and  $\delta_2$  are the mean change from baseline in the monthly average number of migraine days for the fremanezumab treatment group and the placebo treatment group respectively.

The primary efficacy endpoint will be analyzed using an analysis of covariance (ANCOVA) model with sex, region (United States, European, or rest of world), migraine classification (ie, CM or EM), baseline PHQ-9 score category (10 to 14, 15 to 19, and  $\geq 20$ ), and treatment as factors and baseline number of migraine days as a covariate. The stratification factors (as randomized) will be used in the model. The least square (LS) mean treatment difference (fremanezumab - placebo), 95% confidence interval (CI) for the LS mean treatment difference, and the associated p-value will be generated from this model.

The statistical test will be two-sided at the alpha=0.05 level of significance. The SAS code for this test is as follows:

```
PROC MIXED;
  CLASS TREAT SEX REGION MIGCLASS PHQCAT;
  MODEL CHG= TREAT SEX REGION MIGCLASS PHQCAT BASE;
  LSMEANS TREAT / DIFF CL;
RUN;
```

The normality assumption for the ANCOVA model will be checked to ensure validity of the primary analysis. If the model assumptions are not met (p-value <0.01), a nonparametric method such as Wilcoxon Rank Sum test will be conducted as a sensitivity analysis.

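### Baseline migraine-preventive use is capped and recorded but is not a term in the primary ANCOVA or its MMRM: a small precision gain forgone, not a bias

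*Protocol*

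**What the plan says.** **Who may take a preventive.** Protocol 5.7 allows one migraine preventive if the dose has been stable for at least 8 weeks before the baseline period. It sets a ceiling: "The total number of patients receiving concomitant migraine preventive medication during the study will not exceed 30% of the total sample size". Inclusion criterion f (Protocol 4.1) repeats the 30% allowance and bars starting a preventive during the study. Indication, dose, and start and end dates go on the eCRF.

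**Randomisation.** Protocol 5.9 and SAP 2.2 stratify by sex, country, migraine classification and PHQ-9 category, and "each patient will be randomized in a 1:1 ratio within the stratum to which he or she belongs". Preventive use is not a factor.

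**Models.** The primary ANCOVA in SAP 6.2.2 is "MODEL CHG= TREAT SEX REGION MIGCLASS PHQCAT BASE". The MMRM in SAP 6.2.3.1 adds month and treatment-by-month. The multiple-imputation analysis and the repeat with actual strata (SAP 6.2.3.2 and 6.2.3.3) use the same covariates. The responder model (SAP 6.3.2.2) has the same factors without baseline migraine days. None has a preventive-use term.

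**Where preventive use does appear.** It is a category in the descriptive summaries of prior medication (SAP 5.5) and concomitant medication (SAP 8.9). It is not among the baseline characteristics in SAP 5.3. The exploratory endpoints are redacted, so these statements cover the visible text only.

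**Sample size.** Protocol 9.1 plans "A sample size of 288 (144 per treatment group) evaluable patients completing the study", for "90% power to detect a treatment difference of 2 days with a common standard deviation of 5.2 days" "at a 2-sided alpha level of 0.05". It adds: "Assuming a 15% drop-out rate, approximately 340 patients (approximately 170 patients per treatment group) will be randomized".

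**The concern.** The protocol treats background prevention as worth controlling: it caps it, requires a stable dose and forbids starting it. For both pivotal Phase 3 studies, Protocol 1.2.2.2 also reports the treatment effect in the 79% of patients who took no preventive. A baseline variable treated this way is a natural candidate for the primary model. If it predicts change in migraine days, leaving it out keeps explainable variance in the residual and lets a chance difference between arms pass into the estimate.

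The planned tables only partly fill the gap. The prior-medication summary takes in everything before the first dose, with up to 10 years of migraine and depression treatment, so it mixes past and current use. The concomitant summary runs to the end of the study. Neither is a clean count of patients on a preventive at baseline.

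Timing matters because a term added after an imbalance has been seen is post hoc. The choice has to be fixed while the data are blinded.

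**Working it through.** **1. Reproduce the plan's figures.** Inputs from Protocol 9.1: difference 2 days, SD 5.2, two-sided alpha 0.05, 144 per arm.
- n per arm for 90% power = 2 × (1.96 + 1.2816)² × 5.2² / 2² = 143 (plan: 144).
- SE of the difference = 5.2 × √(2/144) = 0.613 day; 95% CI half-width = 1.96 × 0.613 = 1.20 days.
- Power at 144 per arm = 0.904 (0.902 from the t distribution; plan: 90%).
- 288 / 0.85 = 339 randomised (plan: about 340).

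The sample size stands, and the omission does not affect it.

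**2. Size of chance imbalance.** Let p be the share of users. The SD of the difference in proportions is √(2p(1 − p)/n).
- p = 0.30 (the cap), n = 144: √(0.42/144) = 0.0540; × 1.96 = ±10.6 percentage points.
- p = 0.21 (the share in both Phase 3 studies, Protocol 1.2.2.2), n = 144: SD 0.0480; ±9.4 points.
- p = 0.30, n = 170 (all randomised): SD 0.0497; ±9.7 points.

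**3. Effect on the estimate and on power.** Let g be the difference in change between users and non-users. **The documents give no value for g; 0 to 3 days is an assumed range.** With p = 0.30 and n = 144:
- 95% range of shift = ± g × 0.1059
- R² = p(1 − p)g² / 5.2² = 0.21g² / 27.04
- adjusted SD = 5.2 × √(1 − R²), with power recomputed from it

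| g (days, assumed) | Shift (days) | R² | Adjusted SE | Power |
|---|---|---|---|---|
| 0 | 0 | 0 | 0.613 | 0.904 |
| 1 | ±0.11 | 0.8% | 0.610 | 0.906 |
| 2 | ±0.21 | 3.1% | 0.603 | 0.912 |
| 3 | ±0.32 | 7.0% | 0.591 | 0.923 |

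Baseline migraine days and migraine classification are already in the model and may absorb part of any effect, so each row is nearer an upper bound for its g.

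**4. Simulation check.** With 10,000 trials for each of g = 0, 1 and 2, the mean unadjusted estimate was −2.00 days every time, which is the true value. Power without and with the term was 0.900 and 0.900 (g = 0), 0.901 and 0.905 (g = 1), and 0.905 and 0.912 (g = 2). The Monte Carlo error of each figure is about 0.003 (√(0.9 × 0.1/10,000)), so this confirms the order of magnitude, not the third decimal.

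**5. Would stratifying be better?** Existing cells: 2 sexes × 13 countries × 2 migraine classes × 3 PHQ-9 categories = 156, or 340/156 ≈ 2.2 patients each. One more binary factor gives 312 cells, or 340/312 ≈ 1.1 patients each. Stratification is not the remedy.

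**6. Can the flag be coded?** Appendix G lists amitriptyline, venlafaxine, nortriptyline and duloxetine both as capped preventives and as antidepressants allowed for everyone. In each list the drug counts even if it was prescribed for another indication. In a population with depression, a yes/no flag is ambiguous without a rule.

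**The case against.** The strongest reply is that the documents show no prognostic effect. A cap may only reflect concern about the population mix. A treatment effect that was also seen in non-users says something about consistency of the effect; it does not say that users and non-users change by different amounts. Doses are stable before baseline, the outcome is a change from baseline, and baseline migraine days and migraine classification are already adjusted for. All of this stands, and it is why every gain above depends on an assumed g.

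A reader might also infer one of the following. The documents support none of them.
- **That the primary estimate is biased.** Under randomisation a chance imbalance is not bias. The standard error already allows for it, and the unadjusted estimate is centred on the truth.
- **That adjustment can only help.** If g is zero, the term uses a degree of freedom and returns nothing.
- **That the gain could be large.** Explaining 5% of the variance needs g = √(0.05 × 27.04/0.21) ≈ 2.5 days, more than the 2-day treatment difference the trial is built to detect.
- **That every model should carry the term.** In the logistic responder model an added covariate changes the conditional odds ratio being estimated and does not reduce the standard error of its logarithm.

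What remains is narrow: a recorded baseline variable could enter the linear models at almost no cost, and the plan does not use it.

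**Conclusion.** The omission is real, and the point is a cheap improvement. It does not threaten the primary conclusion or the sample size. At 30% use and 144 per arm, the 95% range of chance imbalance is about ±10.6 percentage points. If users and non-users differ by 1 to 2 days, the possible shift is about 0.1 to 0.2 day, against a CI half-width of 1.20 days, and power would rise from 0.904 to about 0.906–0.912. With no such difference the gain is zero. The results rest on the assumed g, on use at the full 30% cap, and on reading 5.2 days as the residual SD without the term.

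A baseline antidepressant term in the HAM-D 17 MMRM (SAP 6.3.1.2) is optional on the same reasoning. As an illustration, assume half the patients take an antidepressant and users differ by 2 points. Then R² = 0.25 × 4/36 = 2.8%, and power would go from 0.807 to about 0.82. Neither input is in the documents. Antidepressants may also be changed during treatment (Protocol 5.7), so a baseline flag captures their use only in part.

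**What to change.** Before unblinding:

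1. **Add the term.** Put baseline migraine-preventive use (yes/no) as a factor in the primary ANCOVA (SAP 6.2.2) and its MMRM (SAP 6.2.3.1). The secondary endpoints borrow that MMRM by reference, so say whether the term carries over to them.
2. **Define a user.** Use the indication recorded on the eCRF for a medication ongoing at baseline. This settles the four drugs on both Appendix G lists. The rule is for analysis only and does not alter who may enrol.
3. **Show baseline use by arm** in the table under SAP 5.3.
4. **Record the change** in SAP Section 11, which now states that there are none.
5. **Optional:** add baseline antidepressant use (yes/no) to the HAM-D 17 MMRM.

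Do not add a stratification factor, and leave the responder model as it is. The cost is one degree of freedom, one coding rule and one table row; no new data are needed.

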5.8. Procedures for Monitoring Patient Compliance

The investigator will be responsible for monitoring patient compliance until completion of the IMP administration according to the protocol or discontinuation from IMP. If the investigator or the sponsor determines that the patient is not in compliance with the study protocol, the investigator and the sponsor should determine whether the patient should be withdrawn from the study. The Independent Ethics Committee/Institutional Review Board (IEC/IRB) should be notified.

5.9. Randomization and Blinding

After the 28-day baseline period, the first 12 weeks of this study will be double-blind. Patients and investigators will remain blinded to IMP assignment during this part of the study. This will be followed by a 12-week open-label extension phase.

Patients will receive 225 mg sc fremanezumab (visit 2, visit 3, and visit 4) or matching placebo (visit 2) in monthly doses.

For the first phase of this study, the sponsor, investigators, study staff, and patients will be blinded to treatment assignment. A computer-generated master randomization list will be provided to drug packaging facilities. The packaging vendor(s) will package active drug and placebo into single-visit kits according to Good Manufacturing Practice procedures. Kits will be identical in appearance and contain 1 prefilled syringe with either active drug or placebo.

Patients will be stratified based on sex, country, migraine classification (ie, CM or EM), and PHQ-9 score category (10 to 14, 15 to 19, and ≥ 20) to ensure balance for the covariates.

Patients will be randomly assigned to treatment groups by means of a computer-generated randomization list using electronic IRT. This system is used to ensure a balance across treatment groups. The specifications for randomization will be under the responsibility and oversight of Teva Global Statistics.

At randomization visit (day 1), each patient will be randomized in a 1:1 ratio within the stratum to which he or she belongs to receive monthly 225 mg sc fremanezumab or placebo, as assigned by the IRT. In the open-label extension phase starting at week 12, however, all patients will receive active treatment with a quarterly dose of 675 mg sc fremanezumab.

The IRT will manage initial drug supply, maintenance of adequate study drug supplies on site, and study randomization centrally. At each study visit where study drug is administered, the IRT will be queried, the site personnel will retrieve the study drug from refrigerated storage, and the patient will self-administer treatment with the 1 or 3 prefilled syringes, depending on the study visit, contained in the appropriately numbered kit.

The sponsor's clinical personnel (and delegates) involved in the study will be blinded to the identity of the IMPs until the database is locked for analysis and the IMP assignment is known. However, if a prioritized sample analysis is needed, bioanalytical and clinical pharmacology personnel may be unblinded.

In the event of an emergency, it will be possible to determine to which treatment group and dose the patient has been allocated by accessing the IRT system. All investigational centers will be provided with details on how to access the system for code breaking at the start of the study. The Medical Monitor or equivalent should be notified following unblinding. Any unblinding of the IMP performed by the investigator must be recorded in the source documents.

The randomization list will be assigned to the relevant treatment groups through a qualified service provider, eg, via IRT system. The generation of the randomization list and management of the IRT system will be done by a qualified service provider under the oversight of the responsible function at Teva.

